7.4.4 Subgroup Analysis of Efficacy Endpoints

All efficacy endpoints (for continuous variables) will be summarized using descriptive statistics, including mean, standard deviation, minimum, Q1, median, Q3 and maximum for each treatment groups by subgroups defined in section [7.8](#)

7.5 Analysis of Safety

All analysis of safety will be presented by treatment group for SAF, unless specified otherwise.

7.5.1 Adverse Events

Following definitions of AE will be used for analysis.

As for definition of TEAE and drug-related adverse events, refer to section [6.2](#)

“Adverse event leading to permanent discontinuation of study drug” are events selected “DRUG WITHDRAWN” checkbox as both or either one of “Action Taken for Study Drug (Mirabegron/Placebo)” and “Action Taken for Study Drug (Tamsulosin)”.

“Death” is event checked “Death” checkbox as detail of serious adverse event.

If the onset day TEAE is missing, then the day will be imputed by 1st of the months. As a result, if the onset date of TEAE is earlier than the first administration date of the study drug for treatment period, then the onset date will be re-imputed by the same date as the first administration date of the study drug for treatment period. If the end date TEAE is missing, then the date will be imputed by last day of the giving months. And if, the month TEAE is missing, then the date will be imputed by 31DEC. As a result, if the end date of TEAE is earlier than the first administration date of the study drug for treatment period, then the onset date will be re-imputed by the same date as the first administration date of the study drug for treatment period. The imputed onset day and end day will be used for summary of AE with time interval (section 7.5.1.4).

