5.5.1.1 Treatment-Emergent Adverse Events (TEAEs)

For the purposes of analysis of the safety data following the completion of the study, a TEAE is defined as follows:

- An AE with onset during the double-blind Treatment period
- An AE with onset during the Screening period, with worsening severity during the double-blind Treatment period

Thus, AEs with onset during the Screening period that either resolved during that period or continued into the double-blind Treatment period with the same or lesser severity will NOT be counted as TEAEs.

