6.2 Safety Variables

Safety will be assessed by evaluation of the following variables:

- Incidence and severity of treatment emergent adverse events (TEAEs)
- Laboratory parameters (serum chemistry, hematology and urinalysis)
- Vital signs: sitting systolic and diastolic blood pressure and pulse rate (home based self-measurements and office measurements)
- Post-void residual (PVR) urine volume
- Maximum urine flow rate (Qmax)

TEAE is defined as an adverse event observed after starting administration of study drug. If the adverse event occurs on Day 1 and the onset check box is marked “Onset after first dose of study drug for the treatment period” or the onset check box is left blank, then the adverse event will be considered treatment emergent. If the adverse event occurs on Day 1 and the onset check box is marked “Onset before first dose of study drug for the treatment period”, then the adverse event will not be considered treatment emergent. If a subject experiences an event both during the screening period and during the treatment period, the event will be considered as TEAE only if it has worsened in severity (i.e. it is reported with a new start date). All adverse events collected that occur within 7 days after taking the last dose of study drug will also be counted as TEAE.

A drug-related TEAE is defined as any TEAE with at least a possible relationship as assessed by the investigator, with ‘not assessable’ or with missing assessment of the causal relationship to both or either one of Mirabegron/Placebo and Tamsulosin.

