7.2.4 Previous and Concomitant Medications

Previous and concomitant medications are coded with WHO-DD, and will be summarized by therapeutic subgroup (ATC 2nd level) and chemical subgroup (ATC 4th level) and preferred WHO name by treatment group for the SAF, FAS and PPS.

As with previous medication, concomitant medication will be summarized for each treatment group by therapeutic subgroup (ATC 2nd level) and chemical subgroup (ATC 4th level) and preferred WHO name for the SAF, FAS and PPS. Subjects taking the same medication multiple times will be counted once per medication. A medication which can be classified into several chemical and/or therapeutic subgroups is presented in all chemical and therapeutic subgroups.

If the start day of concomitant medications/therapy is missing, then the day will be imputed by 1st of the months. As a result, if the start day of concomitant medications/therapy is earlier than the first administration date of the study drug for treatment period, then the onset date will be re-imputed by the same date as the first administration date of the study drug for treatment period. If the end day of concomitant medications/therapy is missing, then the day will be imputed by last of the months. As a result, if the end date of concomitant medications/therapy is earlier than the first

administration date of the study drug for treatment period, the end date will be re-imputed by the same date as the first administration date of the study drug for treatment period.

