7.5.1.7 AEs Reported During Screening Period by SOC and/or PT

The number and percentage of subjects with AEs reported during screening period, as classified by SOC and PT will be summarized for each treatment group. Summaries will be provided for:

- AEs,
- serious AEs.

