7.10.1 Missing Data

The final handling of missing data will be decided by the time of database lock, and will be based on the opinion and advice of a medical expert.

As a general principle, no imputation of missing data for other variables will be done. Exceptions are the start and stop dates of AEs and concomitant medication.

The imputed dates will be used to allocate the concomitant medication and AEs to a treatment group, in addition to determining whether an AE is/is not treatment emergent. Listings of the AEs and concomitant medications will present the actual partial dates; imputed dates will not be shown.

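### SAP 7.5.1 and 7.10.1 disagree on whether TEAE status comes before or after date imputation; if after, the reset to first dose needs a same-month condition

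*SAP*

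**What the plan says.** **Onset (SAP 7.5.1).** "If the onset day TEAE is missing, then the day will be imputed by 1st of the months". If the result is before first dose, "then the onset date will be re-imputed by the same date as the first administration date of the study drug for treatment period". The only comparison is with the first-dose date; nothing requires the recorded month to be the first-dose month. The section names one use for the imputed dates, the time-interval summary.

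**End (SAP 7.5.1).** A missing end is set to the last day of the month, or to 31 December if the month is missing. Then, "if the end date of TEAE is earlier than the first administration date", the clause moves the onset, not the end, to first dose.

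**Use (SAP 7.10.1).** Imputed dates allocate adverse events and concomitant medication to a treatment group, "in addition to determining whether an AE is/is not treatment emergent".

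**Definition (SAP 6.2).** "TEAE is defined as an adverse event observed after starting administration of study drug". A check box settles events on Day 1. There is no rule for a partial onset date.

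**Protocol 5.5.1.1.** "AEs with onset during the Screening period that either resolved during that period", or carried on without worsening, are not TEAEs. SAP 7.5.1.7 tabulates "subjects with AEs reported during screening period" separately.

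**Medication (SAP 7.2.4).** The start rule has the same unconditional reset. If an imputed stop is before first dose, "the end date will be re-imputed by the same date as the first administration date of the study drug for treatment period". SAP 6.3 calls a drug concomitant if any dose falls between first and last dose, inclusive.

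SAP 7.10 refers to a data specification document for more detail. It is not among the documents.

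**The concern.** TEAE status is an input to imputation in SAP 7.5.1 and an output of it in 7.10.1. A programmer must choose which section governs, and neither choice is complete. One can place events known to predate treatment in the TEAE tables; the other leaves some events undecided.

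TEAE incidence and severity is a listed safety variable, and TEAE status feeds the overview, the SOC and PT tables, the Fisher tests and the 2.0% frequency threshold in SAP 7.5.1. What is at stake is the accuracy of absolute TEAE and concomitant-medication rates and agreement with the protocol's definition.

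**Working it through.** The plan gives no figure on this point, so there is nothing to reproduce. The check is logical, with a count of days to show where the rules bite.

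**1. Reading A: status first (SAP 7.5.1).** Take an event with a missing onset day and compare its known month with the first-dose month.
- Earlier month: onset precedes first dose, so it is not a TEAE under 6.2 and never reaches the reset.
- Later month: a TEAE whatever the day.
- Same month: 6.2 needs the day, which is missing. No rule decides, unless first dose was on the 1st.

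**2. Reading B: imputed date decides (SAP 7.10.1).** Example with first dose on 20 March 2016:

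| Recorded onset | Imputed | After reset as written | With same-month condition |
|---|---|---|---|
| February 2016 | 1 Feb | 20 Mar, TEAE | 1 Feb, not TEAE |
| March 2016 | 1 Mar | 20 Mar, TEAE | 20 Mar, TEAE |
| April 2016 | 1 Apr | 1 Apr, TEAE | 1 Apr, TEAE |

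Only the February row changes, and it is the one that conflicts with protocol 5.5.1.1.

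**3. Does the check box prevent this?** It applies to Day 1, which SAP 7.10.3 defines as the prescription day. Protocol 5.1.5 starts dosing the day after dispensing. A reset onset therefore normally falls on Day 2, outside the check-box rule.

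**4. End dates.** If the last day of a month or year precedes first dose, so does every day in it. The end-date clauses therefore act on an imputed end only when the record really ended before first dose.
- Adverse events: the clause is inert under reading A. Under reading B it moves the onset to first dose and leaves the end before the onset.
- Drugs: a stop recorded as May 2016, with first dose on 20 June 2016, is imputed to 31 May and then moved to 20 June. Used for classification, that date meets the concomitant definition. Protocol 5.1.3.2 records drugs from Visit 1, so drugs stopped during screening will be in the data.

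**5. Shares of days.** Assumption: first-dose dates uniform from 1 January 2016 to 8 June 2017 (525 dates), so that 84 treatment days fit within the planned end of August 2017. The screening period is the L days before first dose, with L = 21, 28 or 35 from the Visit 1 window of Day -35 to Day -21.

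Share in an earlier month = (date, day) pairs in an earlier calendar month than first dose / (525 × L).

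| L | Earlier month | Share | First-dose month |
|---|---|---|---|
| 21 | 4,067 / 11,025 | 36.9% | 63.1% |
| 28 | 7,098 / 14,700 | 48.3% | 51.7% |
| 35 | 10,738 / 18,375 | 58.4% | 41.6% |

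If first dose is the day after Visit 2 and screening days are counted back from Visit 2 (Visit 2 on each day from 10 January 2016 to 31 May 2017), the earlier-month shares are 38.7%, 50.3% and 60.2%.

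Treatment days: 525 × 84 = 44,100. Of these, 18.9% lie in the first-dose month. In 7,791 (7,791 / 44,100 = 17.7%) the 1st of the month precedes first dose, so the day is ambiguous; the rest belong to first doses on the 1st.

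Deleting the onset reset altogether would lose those 7,791 treatment days as TEAE onsets. The same-month condition loses none, by construction.

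**The case against.** **The wording of 7.5.1 limits its own reach.** Its adverse-event imputation sentences act on a TEAE, the section sends the definition to 6.2, and it uses the dates only for time intervals. Read alone, the reset merely prevents a negative study day. That is fair, and it is why the harm to TEAE counts is conditional. But 7.10.1 gives the imputed dates a different use, and reading A still leaves first-dose-month events undecided.

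**The data specification document may hold the rule.** It may, and the effect would then be nil. It would not remove the conflict between two sections of the SAP.

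**Date is not the only evidence.** Adverse events are assessed at Visit 2, before randomization and dosing, so an event recorded then is pre-treatment whatever its date. This could rescue many cases, but the SAP does not say that visit of record is used.

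**Stronger inferences do not hold.** A reader might infer that screening events in general enter the TEAE tables, or that every drug stopped in screening becomes concomitant. The reset follows imputation of a missing date part, so complete dates are untouched. Nor does 48% mean that about half of screening events are misclassified: it is a share of calendar days, and the documents give no count of partial dates. Bias between arms is not supported either, because screening precedes randomization and the rule is the same in both arms.

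**Conclusion.** The point holds as a minor defect. SAP 7.5.1 and 7.10.1 give TEAE status opposite places in the sequence. If 7.10.1 governs, a stated rule gives a wrong result for events with a missing onset day and a recorded month before the first-dose month. If 7.5.1 governs, events with a missing day in the first-dose month have no rule. The stop-date clause in 7.2.4 gives a wrong concomitant status if its dates are used for classification, and the end-date clause in 7.5.1 moves the onset where the end appears to be meant.

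The effect on counts cannot be sized. It is nil if dates are complete or the data specification document already settles the matter. The day shares rest on the assumed even spread of first-dose dates and show only where a partial date would be affected. The harm is to absolute TEAE and medication rates; primary efficacy is not involved.

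**What to change.** 1. Make SAP 6.2, 7.5.1 and 7.10.1 agree that partial dates are imputed for all adverse events before TEAE status is assigned.
2. Reset an imputed onset (7.5.1) or drug start (7.2.4) to first dose only if the known month and year equal those of first dose, or the year if only the year is known, and no known end date precedes first dose. Otherwise leave the imputed date unchanged.
3. Delete the end-date re-imputation clauses in 7.5.1 and 7.2.4.
4. State that the check box for onset before first dose, now limited to Day 1 in 6.2, is extended to partial onset dates where it was completed. This is a new use and should be declared.
5. If the data specification document already has such rules, copy them into the SAP.
6. Editorial: the time-interval cross-reference in 7.5.1 should be 7.5.1.5, not 7.5.1.4.

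Downside: a screening onset with a missing day in the first-dose month still counts as a TEAE unless the check box or an end date shows otherwise. Those are the first-dose-month days in the table above, 51.7% of a 28-day screening period. This is conservative.

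Cost: a few sentences and a small program change before unblinding. No new data.

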7.5.1.1 Adverse events

An overview table will include the following details:

- Number of TEAEs,
- Number and percentage with two-sided 95% CI of subjects with TEAEs,
- Number of drug related TEAEs (Mirabegron/Placebo, Tamsulosin, Both),
- Number and percentage with two-sided 95% CI of subjects with causally drug related TEAEs (Mirabegron/Placebo, Tamsulosin, Both),
- Number of serious TEAEs,
- Number and percentage with two-sided 95% CI of subjects with serious TEAEs,
- Number of serious drug related TEAEs (Mirabegron/Placebo, Tamsulosin, Both),
- Number and percentage with two-sided 95% CI of subjects with serious drug related TEAEs (Mirabegron/Placebo, Tamsulosin, Both),
- Number of TEAEs leading to permanent discontinuation of study drug (Mirabegron/Placebo, Tamsulosin, Both),
- Number and percentage with two-sided 95% CI of subjects with TEAEs leading to permanent discontinuation of study drug (Mirabegron/Placebo, Tamsulosin, Both),
- Number of drug related TEAEs leading to permanent discontinuation of study drug* (Mirabegron/Placebo, Tamsulosin, Both),
- Number and percentage with two-sided 95% CI of subjects with drug related TEAEs leading to permanent discontinuation of study drug (Mirabegron/Placebo, Tamsulosin, Both),
- Number of serious TEAEs leading to permanent discontinuation of study drug (Mirabegron/Placebo, Tamsulosin, Both),
- Number and percentage with two-sided 95% CI of subjects with serious TEAEs leading to permanent discontinuation of study drug (Mirabegron/Placebo, Tamsulosin, Both),
- Number of serious drug related TEAEs leading to permanent discontinuation of study drug (Mirabegron/Placebo, Tamsulosin, Both),

- Number and percentage with two-sided 95% CI of subjects with serious drug related TEAEs leading to permanent discontinuation of study drug (Mirabegron/Placebo, Tamsulosin, Both) and
 - Number of deaths.
- *: Categorization of drug related TEAEs leading to permanent discontinuation of study drug (Mirabegron/Placebo, Tamsulosin, Both) will be defined as events matching to the category for both relationship to study drug and action taken for study drug at the same time.

The treatment groups will be compared using Fisher's Exact test, with a two-sided 95% exact unconditional CI (point estimate will be calculated as [Mirabegron + Tamsulosin] minus [PLACEBO + Tamsulosin]) and 5% significance level.

7.5.1.2 Adverse events by SOC and/or PT

The coding dictionary for this study will be MedDRA (ver.18.1), which will be used to summarize AEs by SOC and PT.

The number and percentage of subjects with TEAEs, as classified by SOC and PT will be summarized for each treatment group. Summaries will be provided for:

- TEAEs,
- drug related TEAEs (Mirabegron/Placebo, Tamsulosin, Both),
- serious TEAEs,
- drug related serious TEAEs (Mirabegron/Placebo, Tamsulosin, Both),
- TEAEs leading to permanent discontinuation of study drug (Mirabegron/Placebo, Tamsulosin, Both),
- drug related TEAEs leading to permanent discontinuation of study drug (Mirabegron/Placebo, Tamsulosin, Both),
- TEAEs excluding serious adverse events that equal to or exceed a threshold of 2.0% in any treatment group, and
- Common TEAEs that equal to or exceed a threshold of 2.0% in any treatment group.

The treatment groups will be compared using Fisher's Exact test, with a two-sided 95% exact unconditional CI and 5% significance level.

7.5.1.3 Severity of AE

The number of TEAEs and the number and percentage of subjects with TEAEs, as classified by SOC and PT will also be summarized by severity. In the subject count, if a subject has multiple TEAEs with the same SOC or PT, but with differing severity, then the subject will be counted only once with the worst severity, however, if any of the severity values are missing then the subject will be counted only once with missing severity. In the adverse event count, the adverse events will be presented in each category they were classified to. Drug related TEAEs (Mirabegron/Placebo, Tamsulosin, Both) will be presented in a similar way.

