7.5.1.4 Relationship of AE

The number of TEAEs and the number and percentage of subjects with TEAEs, as classified by SOC and PT will also be summarized by relationship to study drug (Mirabegron/Placebo, Tamsulosin). In the subject count, if a subject has multiple TEAEs

with the same SOC or PT, but with differing relationship, then the subject will be counted only once with the highest degree of relationship. In the adverse event count, the adverse events will be presented in each category they were classified to.

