7.5.1.8 Severity of AEs Reported During Screening Period

The number of TEAEs and the number and percentage of subjects with AEs reported during screening period, as classified by SOC and PT will also be summarized by severity. The method used for this analysis will be identical to the analysis described in section

[7.5.1.3](#)

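### The SAP severity rule can move a subject with a known severe event into the missing row, understating the number of subjects with severe TEAEs

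*SAP*

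**What the plan says.** SAP 7.5.1.3 tabulates TEAEs by SOC, PT and severity, both as events and as subjects. The subject count has a default and an override. The default covers a subject whose repeated events under one SOC or PT were rated differently: "then the subject will be counted only once with the worst severity". The override is that "if any of the severity values are missing then the subject will be counted only once with missing severity".

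The event count is handled separately: "In the adverse event count, the adverse events will be presented in each category they were classified to".

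The same handling extends to two further tables. For related events, "Drug related TEAEs (Mirabegron/Placebo, Tamsulosin, Both) will be presented in a similar way". For screening-period AEs, SAP 7.5.1.8 points to 7.5.1.3 with the words "The method used for this analysis will be identical to the analysis described in section".

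Protocol 5.5.4 has the investigator rate each AE as mild, moderate or severe, and Protocol 7.5.1 plans the tabulation on those three levels. The protocol has no rule for a missing rating. SAP 7.10.1 limits imputation to AE and medication dates, so a blank severity stays blank.

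**The concern.** The override treats every blank as making the subject's worst severity unknown. That is true when the known ratings are mild or moderate. It is not true when one of them is severe, because nothing on the scale is higher. In that case the rule discards an established fact and reports the subject as missing.

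SOC rows are more exposed than PT rows, because a blank on a different term in the same class is enough to trigger the override. As an illustration, the Japanese labelling table in Protocol 1.4.1.1 places tachycardia and palpitations together under cardiac disorders. A subject with severe tachycardia and an unrated palpitation would leave the severe row for that class.

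At stake is a descriptive safety table. Incidence and severity of TEAEs comes first among the safety variables in Protocol 2.3.4 and SAP 6.2, and supports the secondary objective. The instruction is explicit, so a programmer who follows it exactly will produce this count.

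**Working it through.** The plan states no figure on this point, so there is nothing to reproduce. The check applies the rule to constructed records and then asks how large the effect could be.

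**1. The rule on four constructed subjects in one row.** These records are illustrative and do not come from the documents.

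| Subject's ratings in the row | SAP rule as written | Severe never overridden (see fix) | Worst known rating |
|---|---|---|---|
| severe, missing | missing | severe | severe |
| severe, mild | severe | severe | severe |
| severe | severe | severe | severe |
| mild, missing | missing | missing | mild |
| **Subjects counted severe** | **2** | **3** | **3** |
| **Subjects counted mild** | **0** | **0** | **1** |
| **Subjects counted missing** | **2** | **1** | **0** |

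The number of severe events is 3 under all three rules. Only the subject count changes. The override can take a subject out of the severe row but never puts one in.

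**2. How often a known-severe subject would move.** Let k be the number of the subject's TEAEs in the row, one of them rated severe. Let m be the chance that each other event lacks a rating, taken as independent. Then

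P(moved to missing) = 1 − (1 − m)^(k−1).

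For example, k = 3 and m = 5% give 1 − 0.95² = 9.75%, shown as 9.8%. The documents give no value for m, so a range is shown.

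| k | m = 0.5% | m = 1% | m = 2% | m = 5% | m = 10% |
|---|---|---|---|---|---|
| 1 | 0 | 0 | 0 | 0 | 0 |
| 2 | 0.5% | 1.0% | 2.0% | 5.0% | 10.0% |
| 3 | 1.0% | 2.0% | 4.0% | 9.8% | 19.0% |
| 4 | 1.5% | 3.0% | 5.9% | 14.3% | 27.1% |

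**3. What one moved subject is worth.** SAP section 4 plans 275 randomized per arm, used here as an approximate denominator for the Safety Analysis Set. One subject is 1/275 = 0.36 percentage points. If 5 subjects in an arm had a severe event in the row (an assumption), losing one changes 5/275 = 1.8% to 4/275 = 1.5%.

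**4. Direction between arms.** Suppose both arms truly have 5 of 275. Moving one mirabegron subject makes the difference, mirabegron minus placebo, −0.36 points. Moving one placebo subject makes it +0.36 points. The rule is the same in both arms, so the sign depends on where the blanks fall.

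**The case against.** The strongest defence is that the rule is transparent and nearly inert. Protocol 5.5.4 calls for a rating of every AE, and Protocol 8.1.1 provides for query resolution and monitoring, so blanks should be rare. A moved subject still appears in a labelled missing row, every severe event stays in the event count, and Protocol 7.5.1 lists all AEs by subject. For the treatment period, Protocol 7.5.1 asks for AEs by severity, which reads as an event count; the subject count there is added by the SAP. All of this stands and limits the importance of the point. It does not make the subject count right for a subject with a severe event and a blank.

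The defence is also right that the missing row is the honest place for a subject whose ratings are mild and blank. Reporting worst known severity throughout would call that subject mild when the unrated event might be severe.

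Three stronger readings are tempting and are not supported:

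- **That severe TEAEs in general are undercounted.** Only the count of subjects is affected.
- **That the error favours mirabegron.** The rule applies to both arms of a double-blind trial, and nothing in the documents suggests that blanks would differ by arm. In the screening period all subjects receive the same treatment.
- **That the rule contradicts the SAP's own conventions.** For relationship, SAP 7.5.1.4 says "then the subject will be counted only once with the highest degree of relationship", and SAP 6.2 counts as drug-related an event "with missing assessment of the causal relationship to both or either one of Mirabegron/Placebo and Tamsulosin". These are more cautious choices for a different variable. The contrast is worth noting, but it is not an inconsistency.

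**Conclusion.** The point holds in a limited form. As written, SAP 7.5.1.3 can understate the number and percentage of subjects with severe TEAEs in an SOC or PT row, in either arm, when a subject has a severe event and an unrated event in the same row. For that subject the worst severity is known, and the tabulated category is wrong.

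The size cannot be derived from the documents. It is probably zero to a few subjects, and exactly zero if no rating is missing. A reader might infer a 20% loss of severe subjects from the 5-to-4 illustration (1/5), but both the 5 and the blank are assumed. The overall TEAE, serious, discontinuation and death counts in SAP 7.5.1.1, and the Fisher tests in 7.5.1.1 and 7.5.1.2, do not use the severity category and are unchanged. Priority is low.

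**What to change.** Amend the override in SAP 7.5.1.3 along these lines: a subject with any event rated severe in that SOC or PT is counted once as severe, regardless of missing values; the missing category is used only when no event is rated severe and at least one severity is missing. Otherwise the worst-severity default applies.

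Apply the same wording to drug-related TEAEs in 7.5.1.3. Screening-period AEs follow through the cross-reference in 7.5.1.8.

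The cost is one sentence in the SAP and one line of programming. It is best done before unblinding, because SAP section 1 requires later changes to the planned analyses to be justified in the Clinical Study Report.
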